2 PURPOSE

The purpose of this statistical analysis plan (SAP) is to ensure that the data listings, summary tables and figures which will be produced, and the statistical methodologies that will be used, are completely specified and appropriate to allow valid conclusions regarding the study objectives.

2.1 Responsibilities

FMD K&L Inc. will perform the statistical analyses and is responsible for the production and quality control of all tables, figures and listings as specified in the SAP. Data Management will be conducted by Numoda, based in Philadelphia, PA. Pharmacokinetic analysis of the study drug will be performed by QPS LLC and NMS, a sub-contractor for ACM will conduct the ConAED PK analysis. The results of ConAED and study drug PK levels will be included in the listing.

2.2 Timings of Analyses

The primary analysis of efficacy, safety, and tolerability is planned after all subjects in Cohort 2 complete the 14-week double-blind (DB) phase of the study. Unless otherwise specified, the analysis includes all DB phase of Cohort 2 data collected in the database through database lock for the DB phase of the study for all subjects randomized.

A follow-up analysis will be conducted when all subjects complete the final visit of the study, which includes a 1-year open-label (OL) phase that follows the 14-week DB phase of the study. Analyses that include data collected after the DB phase database lock from the primary analysis of the study will be issued as an addendum to the study report.

3 STUDY OBJECTIVES

3.1 Primary Objective

To evaluate efficacy of ganaxolone compared to placebo as adjunctive therapy in adults with partial-onset seizures (POS), with or without secondary generalization.

3.2 Secondary Objectives

To evaluate the safety and tolerability of ganaxolone compared to placebo as adjunctive therapy in adults with POS, with or without secondary generalization.

To evaluate pharmacokinetics of ganaxolone at 1200 mg/d and 1800 mg/d after chronic dosing.

To evaluate the safety and tolerability of ganaxolone when administered as adjunctive therapy in adults with POS, with or without secondary generalization, over a 12-month period.

3.3 Brief Description

This is a 2-cohort study with each cohort comprised of 2 phases, a DB phase (Phase 1) followed by an OL phase (Phase 2). Cohort 1 will provide efficacy, tolerability, safety, and PK

information for ganaxolone 1200 mg/d, 1800 mg/d compared to placebo. Cohort 2 will investigate the efficacy, tolerability and safety of ganaxolone 1800 mg/d compared to placebo. Cohort 1 (N = approximately 50) will enroll into a 67-week protocol comprising a 4-week retrospective and 4-week prospective baseline period and 2 treatment phases: a 9-week DB phase followed by a 52-week OL phase. Cohort 2 (N = 292) will enroll into a 76-week study comprising an 8-week prospective baseline period and 2 phases: a 14-week DB phase followed by a 52-week OL phase. In each cohort, the final safety assessment will be conducted 2 weeks following the end of the OL phase.

Baseline seizure activity will be determined by 8 weeks of recording in subject daily seizure calendars. In Cohort 1, the 8 weeks are obtained from a 4-week retrospective baseline period and a 4-week prospective baseline. The baseline for Cohort 2 is an 8-week prospective baseline, though some subjects randomized into Cohort 2, under Protocol version Amendment 2, will have baseline comprised of 4 weeks retrospective and 4 weeks prospective data. After completing the 8-week baseline period, eligible subjects will be randomized to receive either ganaxolone or placebo.

Cohort 1, Phase 1 of treatment includes a 9-week DB placebo-controlled phase to evaluate oral study medication as add-on therapy in adults with epilepsy consisting of POS, with or without secondary generalization. Study subjects will be randomized to one of the 2 study treatment arms: ganaxolone (1200 mg/day (mg/d) followed by 1800 mg/d), or placebo. Phase 1 (DB phase) is comprised of a Baseline period (8 weeks; 4 weeks retrospective and 4 weeks prospective seizure calendar data to be used for baseline assessment), followed by 2 treatment periods: Titration (1 week; step titration up to 1200 mg/d) and Maintenance (8 weeks; 4 weeks on 1200 mg/d followed by 4 weeks on 1800 mg/d).

Between DB (Phase 1) and OL (Phase 2) study phases, Cohort 1 has a 1-week, double-blinded, step transition for placebo subjects to 900 mg/d followed by 1800 mg/d while ganaxolone subjects are maintained on their current dose. For the purpose of entering dosing information on the eCRFs, the sites are instructed to assume that all patients transitioning to the OL phase are on placebo and will enter dose-escalation information accordingly. After unblinding K&L will correct the actual dosing, and the patients who were on ganaxolone during the DB phase will be changed to have received 1800 mg/day during the transition period.

Cohort 1, Phase 2 is the OL phase, consisting of 2 treatment phases: Flexible Dosing (51-week flexible dosing during which time the dose may be adjusted based on efficacy and tolerability guidelines), and De-escalation (2 weeks, at study termination). Subjects discontinued during the study will be de-escalated over 2 weeks based on dose, duration, and tolerability in the opinion of the investigator.

Cohort 2, Phase 1 of treatment includes a 14-week DB phase placebo-controlled treatment period to evaluate oral study medication as add-on therapy in adults with epilepsy consisting of POS, with or without secondary generalization. Study subjects will be randomized to one of the 2 study treatment arms: ganaxolone at 1800 mg/d or placebo. Phase 1 (DB phase) is comprised of a Baseline period (8 weeks), followed by 2 treatment periods: Titration (2 weeks up to 1800 mg/d) and Maintenance (12 weeks on 1800 mg/d). Subjects entered into Cohort 2, under

Protocol Amendment 2, will have a baseline assessment based on 4 weeks retrospective and 4 weeks prospective seizure data.

Between the study phases, Cohort 2 has a 2-week, blinded, step transition for placebo subjects to ganaxolone, starting at 900 mg/d to 1800 mg/d, while ganaxolone subjects are maintained on their current dose. For the purpose of entering dosing information on the eCRFs, the sites are instructed to assume that all patients transitioning to the OL phase are on placebo and will enter dose-escalation information accordingly. After unblinding K&L will correct the actual dosing, and the patients who were on ganaxolone during the DB phase will be changed to have received 1800 mg/day during the transition period.

Cohort 2, Phase 2 is the OL Phase consisting of 2 treatment periods: Flexible Dosing (50-week flexible dosing during which time the dose may be adjusted between 900 – 1800 mg/day based on efficacy and tolerability), and De-escalation (2 weeks, at study termination). Subjects discontinued during study will be de-escalated over 2 weeks based on dose, duration, and tolerability in the opinion of the investigator.

At all dose levels, ganaxolone capsules or matching placebo will be administered BID in divided doses. Subjects will maintain seizure calendars to record the number and type of seizures throughout the entire study. Subjects will also record concomitant medications and any errors in study medication dosing in their seizure calendars.

A graphic representation of the design of this study is provided in SAP [Section 3.8, Figure 1](#) and [Figure 2](#).

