9.4.5 Study Dosing and Dosage Adjustments

Double-blind Phase:

Cohort 1: The study drug dose will be titrated from 400 mg/day to 1200 mg/day in divided doses BID by the end of Week 1 and maintained to Week 5. Dosage will be increased to 1800 mg/day Week 6 and maintained through Week 9 (Table 1).

Cohort 2: The study drug dose will be titrated from 450 mg/day to 1800 mg/day in divided doses BID by the end of Week 2 and maintained through Week 14 (Table 2).

Both titration schedules are consistent with acceptable starting doses and MTDs from previous ganaxolone studies.

Open-Label Phase: Following the completion of the double-blind (DB) phase in either cohort, subjects randomized to placebo will transition to ganaxolone while subjects randomized to ganaxolone will stay on 1800 mg/d. Cohort 1 placebo subjects will begin the 1-week dose titration to 1800 mg/d after completing their Visit 5. Subjects will receive ganaxolone 900 mg/d in divided doses BID for 2 days and step up to 1350 mg for 3 days and then increase to 1800 mg in divided doses BID for 2 days until their Visit 6 (Table 1). Titration for Cohort 2 placebo subjects will mirror the DB phase. Subjects will begin the 2-week dose titration to 1800 mg/d after completing their Visit 5. Subjects will start with 450 mg/d in divided doses BID for 3 days, 900 mg/d in divided doses BID for 3 days, 1350 mg/d in divided doses BID for 4 days, and 1800 mg/d in divided doses BID for 4 days until their Visit 6 (Table 2). At Visit 6, all subjects in both cohorts will be evaluated for tolerability and the investigator will make the determination to maintain the subject on 1800 mg/d or adjust their dose. If the patient experiences any tolerability issues during the transition to OL, such as sedation or dizziness, changes to the titration schedule (e.g., conducting the titration over 3 weeks vs. 2 weeks) may be approved after discussion with the medical monitor. Subjects may be maintained on the MTD of ganaxolone that provides adequate seizure control that is not less than 900 mg/d and not more than 1800 mg/d. Doses may be adjusted upward or downward in 225 mg/d increments every 3 days to reach an optimal dose level over the duration of the 52-week OL phase. Dose adjustments should be made with the investigator's agreement. Frequency of dosing changes may not be less than 3 days unless required for safety.

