9.5.3 Safety Assessments

Planned safety assessments include:

Neurological and physical examinations

Clinical laboratory tests

12-lead ECG

Vital signs including temperature, blood pressure, pulse rate, respiration rate, height, weight and BMI

Columbia Suicide Severity Rating Scale (C-SSRS)

AE monitoring: frequency, severity, duration, causality, outcome

Clinical labs, vitals and ECG measurements may be repeated if needed to corroborate or refute abnormal findings. Both the original and replicate assessments should be recorded in the eCRF.

See [Appendix 1](#) Schedule of Events for timing of Safety Assessments.

Adverse events will be presented for these time periods for Cohorts 1 & 2: ganaxolone vs placebo Titration + Maintenance (Cohort 1: Weeks 1-9, Cohort 2: Weeks 1-14), 1200

mg/d vs placebo (Cohort 1: Weeks 2-5), and 1800 mg/d vs placebo (Cohort 2: Weeks 6-9) for the safety population; open-label (Cohort 1: Weeks 10-61, Cohort 2: 15-66). In addition, tolerability of ganaxolone during the up-titration phases of the study will be compared between the two cohorts. AEs with onset during the titration phase in Cohort 2 will be compared to AEs with onset during the weeks 1-5 in Cohort 1 (1 week titration + 4 week treatment with 1200 mg/day). In addition, in Cohort 2, AEs with onset during the titration phase will be compared to AEs with onset during the maintenance phase. AEs that emerge during the de-escalation period will be tabulated to investigate whether discontinuation of ganaxolone is associated with withdrawal symptoms. Secondary safety outcome measures include those listed below.

Secondary Safety Parameters for Cohorts 1 & 2	Cohort 1		Cohort 2		Combine Cohorts 1 & 2	
	DB Phase	OL Phase	DB Phase	OL Phase	DB Phase	OL Phase
Number of subjects at each dose	X	X	X	X		X
The frequency and proportion of subjects with AEs	X	X	X	X		X
Severity of AEs	X	X	X	X		X
AEs leading to DC	X	X	X	X		X
Incidence of subjects with early DC	X	X	X	X		X
Change from baseline in vital signs (blood pressure, respiration rate and heart rate), body weight and ECG	X	X	X	X		X
Change in clinical hematology and chemistry parameters	X	X	X	X		X
Assessment of suicidality via the Columbia Suicide Severity Rating Scale (C-SSRS)	X	X	X	X		X

Additional assessments may be conducted as considered appropriate.

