- i) Patient Global Impression of Change – Improvement (PGI-I; Patient/Caregiver) at each assessment visit
- j) Clinical Global Impression of Change – Improvement (CGI-I; Investigator) at each assessment visit

Exploratory endpoint

[REDACTED]

[REDACTED] except that the primary endpoint and 50% responder rate will be analyzed the same way as in Cohort 2.

The other primary and secondary efficacy outcome measures will be assessed descriptively for the time periods listed below in Cohort 1 DB phase ([a-e] below) and Cohort 1 + Cohort 2 OL ([f below]):

- a) Ganaxolone Titration + Maintenance 1200 mg/day + Maintenance 1800 mg/day vs Placebo (Cohort 1: Weeks 1 to 9).

- b) Ganaxolone Maintenance 1200 mg/day + Maintenance 1800 mg/day (Cohort 1: Weeks 2-9) vs Placebo (Cohort 1: Weeks 1 to 9).
- c) Ganaxolone Titration + Maintenance 1200 mg/d (Cohort 1: Weeks 1-5) vs placebo (Cohort 1: Weeks 1 to 9).
- d) Ganaxolone Maintenance 1800 mg/d (Cohort 1: Weeks 6-9) vs placebo (Cohort 1: Weeks 1 to 9).
- e) Ganaxolone maintenance 1200 mg/d vs placebo (Cohort 1: Weeks 2 to 5).
- f) OL (Cohort 1: Weeks 10 to 61; Cohort 2: Weeks 16 to 66).

8.2.2 Change from Baseline in 28-day Seizure Frequency and Change from Baseline in 28-day Seizure Frequency for different subtypes of seizures (SPS, SPS-motor, CPS, SGTC)

A rank analysis of covariance (ranked ANCOVA) will be performed. A nonparametric rank analysis of covariance will be used to analyze rank of change from baseline in 28-day seizure frequency, with treatment and pooled center (either US or ROW) as factors and the rank of baseline 28-day seizure frequency as a covariate in the model. The baseline, post-baseline, and change from baseline in 28-day seizure frequency will be summarized by treatment group by using descriptive statistics. The 95% confidence interval of the median by treatment group will also be presented. The 2-sided significance level of 0.05 will be used for comparison. Hodges–Lehmann estimator of the difference in medians together with 95% confidence interval (CI) will be calculated.

Summary table with descriptive statistics will be provided in OL phase for Cohort 1,2, and the combined 2 cohorts. The baseline is the same as for the DB phase.

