9.1 Extent of Exposure

Exposure information will be calculated from the study drug log. Capsule level accountability is not being collected, so exposure to study medication will be summarized as a continuous variable, via the number of days of drug taken. Ganaxolone will be administered BID following the morning and evening meals. Doses should be taken just before or up to 2 hours after a meal or snack, with 240 mL (8 oz.) of water. Each dose should be separated by a minimum of 8 hours and a maximum of 12 hours. A missed dose of study medication may be taken later up to 8 hours before the next scheduled dose; otherwise, the missed dose should not be given.

Exposure data will be summarized using the Safety population for both cohorts.

See tables below for the titration schedules for the transition from DB to OL for both cohorts:

Cohort 1, Phase 2 - Open-Label					
DB Transition to OL					
Visit	Study Day	Dose (mg)/day		Bottle A 225 mg or PBO cap/day	Bottle B 225 mg or PBO cap/day
				GNX: 225mg	GNX: 225mg
		GNX/GNX	PBO/PBO	PBO: 225mg	PBO: PBO
Visit 5	64	1800	900	4	4
	65	1800	900	4	4
	66	1800	1350	6	2
	67	1800	1350	6	2
	68	1800	1350	6	2
	69	1800	1800	8	0
	70	1800	1800	8	0

Cohort 2, Phase 2 - Open-Label					
DB Transition to OL					
Visit	Study Day	Dose (mg)/day		Bottle A 225 mg or PBO cap/day	Bottle B 225 mg or PBO cap/day
				GNX: 225mg	GNX: 225mg
		GNX/GNX	PBO/PBO	PBO: 225mg	PBO: PBO
Visit 5	99	1800	450	2	6
	100	1800	450	2	6
	101	1800	450	2	6
	102	1800	900	4	4
	103	1800	900	4	4
	104	1800	900	4	4
	105	1800	1350	6	2
	106	1800	1350	6	2
	107	1800	1350	6	2
	108	1800	1350	6	2
	109	1800	1800	8	0
	110	1800	1800	8	0
	111	1800	1800	8	0
	112	1800	1800	8	0

These schedules will be used to calculate the exposure for placebo subjects.

Exposure to study medication and cumulative number of days on study medication will be summarized in the DB phase and OL phase for both Cohort 1 and Cohort 2. A summary table of overall exposure to study medication combining the DB phase with OL phase in both Cohort 1

and Cohort 2 will be provided. Ganaxolone group in Cohort 1 will be separated into 2 groups by dose level which are Ganaxolone 1200 mg and Ganaxolone 1800 mg.

A summary table of subjects who reached and maintained maintenance dose of 1800 mg will be provided in each treatment phase for both cohorts. Study drug dosing will be listed.

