Adverse events will be summarized by treatment group and overall for each cohort and phase separately for subjects in the Safety Population. In Cohort 1 tables, AE's will be summarized by treatment, dose level, and overall for subjects in the Safety Population, adverse events of subjects pooled in Cohort 1 and Cohort 2 for each treatment phase will be summarized. The following AE tables will be generated:

- An overall summary of the number and percentage of subjects reporting AEs, serious SAEs, treatment-related AEs, AEs leading to treatment discontinuation and AEs leading to death
- AEs overall and by system organ class and preferred term
- AEs by maximum severity, overall and by system organ class and preferred term
- AEs by relationship to study treatment, overall and by system organ class and preferred term
- AEs with onset (or worsening) during titration + 1200 mg/day dose (weeks 1 to 5) and 1800 mg/d (weeks 6 to 9) by preferred term in Cohort 1 DB phase
- AEs with onset (or worsening) during titration phase and maintenance phase by preferred term in Cohort 2 DB phase
- AEs with onset (or worsening) during the de-escalation phase (time interval between Pre-Taper/Early Termination visit and Post-Taper Safety Follow Up visit) by preferred term in Cohort 1 and 2 OL phase

All AEs, SAEs, AEs leading to drug discontinuation and AEs leading to death will be listed.

Missing date will be imputed followed table describes how missing date information will be handled:

Partial Missing Start or Stop Date	Imputed Start Date	Imputed Stop Date
Missing month and day, and the year is present	January 1 of that year or first dose date if the year is the same as the year of first dose date	December 31 of that year
Missing day, but year and month are present	First day of that month or first dose date if the year and month are the same as the year and month of first dose date	Last day of that month
Missing month, but year and day are present	Missing month imputed as January	Missing month imputed as December

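### The SAP does not settle which phase the blinded switch to ganaxolone belongs to, and it takes former placebo subjects' doses in the switch from the planned schedule

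*SAP*

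**What the plan says.** **Where the switch sits.** For Cohort 2, SAP 3.3 states: "Between the study phases, Cohort 2 has a 2-week, blinded, step transition for placebo subjects to ganaxolone". It describes Cohort 1's one-week switch in the same way. It then describes the OL phase without the switch: "Cohort 2, Phase 2 is the OL Phase consisting of 2 treatment periods: Flexible Dosing" is the first period and de-escalation the second. Protocol 9.1 instead makes the transition the first of three periods within Phase 2, the OL phase.

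**How AEs are tabulated.** SAP 9.3: "Adverse events will be summarized by treatment group and overall for each cohort and phase separately for subjects in the Safety Population". It gives no calendar or study-day boundary between phases. For AEs, Protocol 9.5.3 does give one: "open-label (Cohort 1: Weeks 10-61, Cohort 2: 15-66". The SAP prints OL weeks only for efficacy (SAP 4.2 and 8.2): "OL (Cohort 1: Weeks 10 to 61; Cohort 2: Weeks 16 to 66".

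**How visits are windowed.** SAP 6.4 bounds each visit window at the mid-points between consecutive scheduled visits. SAP 9.4 takes the last laboratory record in a window for the summary tables.

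**How transition doses are set.** Sites enter every subject's doses as if the subject had been on placebo. After unblinding, "the patients who were on ganaxolone during the DB phase will be changed to have received 1800 mg/day during the transition period" (SAP 3.3). SAP 9.1 prints the nominal transition tables and adds: "These schedules will be used to calculate the exposure for placebo subjects". The same section says exposure comes from the study drug log and does not say which source prevails. Protocol 9.4.5 provides that, for tolerability problems in the transition, "changes to the titration schedule (e.g., conducting the titration over 3 weeks vs. 2 weeks) may be approved after discussion with the medical monitor".

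**The concern.** The switch is when every former placebo subject who continues first takes ganaxolone, and Protocol 9.4.5 itself anticipates sedation or dizziness there. Up-titration tolerability is a stated safety comparison (SAP 4.3). SAP 9.3 plans onset tables for double-blind (DB) titration, maintenance and de-escalation, but none for the transition.

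If the phase is not fixed, two programmers following the SAP could produce different by-phase AE tables. The treatment-emergent definition does not help. It runs from the first dose of study medication, which for these subjects is placebo, so it does not mark the start of ganaxolone.

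The dose rule raises a second problem. A subject whose titration was slowed for tolerability would be credited with the planned doses, so the dose summaries would be wrong for the very subjects in whom tolerability was the issue.

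**Working it through.** **1. Number entering the switch.** SAP 3.4 plans about 356 Cohort 2 subjects, 10% discontinuation and 320 completers. Protocol 9.3.1 gives 359, with the same rate and the same 320. Allocation is 1:1, and only completers may enter OL (Protocol 9.2).

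- Plan's own figure: 356 × 0.90 = 320.4, reproducing 320 (359 × 0.90 = 323.1).
- Cohort 2 placebo completers: 320.4 / 2 = 160.2, or 323.1 / 2 = 161.6.
- Cohort 1 has no stated dropout rate. Assuming 10% on 46 subjects: 46 × 0.90 / 2 = 20.7.
- Both cohorts: 160.2 + 20.7 = 180.9, or 161.6 + 20.7 = 182.3. With the SAP's 50 for Cohort 1 and 359 for Cohort 2: 409 × 0.90 / 2 = 184.1.
- Cohort 2 alone (359 randomised) at other dropout rates: 171 at 5%, 153 at 15%, 144 at 20%.

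**2. Which phase the arithmetic implies.** Both documents give a 52-week OL phase.

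- Cohort 2: 50 weeks flexible dosing + 2 weeks transition = 52.
- Cohort 1: 51 + 1 = 52.
- De-escalation cannot supply the missing weeks, because Protocol section 6 counts it separately: 8 + 14 + 52 + 2 = 76 weeks (Cohort 2) and 4 + 9 + 52 + 2 = 67 weeks (Cohort 1).
- Protocol 9.5.3 window: Weeks 15–66 is 66 − 15 + 1 = 52 weeks; Weeks 10–61 is 61 − 10 + 1 = 52 weeks. Both include the transition.

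| Source | Transition in OL? | Cohort 2 transition days (99–112) without a phase |
|---|---|---|
| SAP 3.3, description of periods | No | 14 of 14 |
| SAP 3.3, 52-week length; SAP 9.1 table headings | Yes | 0 |
| Protocol 9.1 and 9.5.3 | Yes | 0 |

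On the literal SAP 3.3 description, 160 × 14 = 2,240 placebo-to-ganaxolone subject-days belong to neither phase.

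**3. Laboratory values.** Visit 5 is at Week 14 (day 98) and Visit 6 at Week 16 (day 112). The mid-point is (98 + 112) / 2 = day 105. An unscheduled or repeat sample on about days 99–105 is therefore in the Visit 5 window. As the last record there, it replaces the end-of-DB value, although a former placebo subject is by then taking ganaxolone. In Cohort 1 the mid-point is (63 + 70) / 2 = day 66.5, so days 64–66 are affected in the same way.

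**4. Doses.**

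- Ganaxolone subjects: Bottles A and B supply 2+6, 4+4, 6+2 or 8+0 capsules, always 8, and 8 × 225 = 1800 mg/day. The recode is right wherever all capsules were taken.
- Placebo subjects, Cohort 2: the nominal table has 10 of 14 days below 1800 mg/day and reaches 1800 on day 109. A subject given the longer titration that Protocol 9.4.5 allows could be credited with 1800 mg/day from day 109 before reaching it. The documents give no detailed longer schedule, so the error in mg cannot be calculated.
- Starting dose: SAP 3.3 and Protocol 9.1 have the Cohort 2 switch start at 900 mg/day. Protocol 9.4.5, Protocol Table 2 and the SAP 9.1 table start it at 450 mg/day.

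**The case against.** The strongest reply is that the question is already answered. SAP 9.1 heads both transition tables as Phase 2, open-label. The 52-week length needs the transition, the protocol puts it in OL and prints an AE window covering every transition day, and SAP section 10 declares no departure from that window. This stands to the extent that the SAP is inconsistent rather than excluding the period. It does not remove the conflict with SAP 3.3 or supply a date rule in SAP 9.3.

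A reader might also infer several stronger things that the documents do not support:

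- **That AEs are lost.** They remain treatment-emergent through the end of study, and SAP 9.3 lists all AEs. Only their place in the by-phase tables is open.
- **That half the Cohort 2 transition is cut off by the Week 16 start.** Days 99–105 do precede Week 16, but the SAP attaches that window to efficacy measures only.
- **That transition AEs will be counted under placebo.** No text carries them back, and the DB phase is fixed at 14 weeks. For laboratory values, by contrast, stated rules can do this.
- **That AEs will be tied to doses not taken.** No Cohort 2 AE table is by dose. SAP 9.3 specifies AEs by dose for the Cohort 1 DB phase and otherwise mentions dose level only for Cohort 1 tables.
- **That recoding to 1800 mg/day is wrong in general.** The capsule arithmetic shows otherwise.

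It can also be said that SAP 9.1 summarises exposure as days of drug taken, so a mg/day error changes that summary little. That is fair. The error falls mainly on the dose-based outputs: the count of subjects at each dose (SAP 4.3) and the table of those who reached 1800 mg and stayed there (SAP 9.1).

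**Conclusion.** The point holds as an inconsistency with practical consequences for safety reporting. SAP 3.3 conflicts with SAP 9.1, with its own 52-week OL length and with the protocol. With no boundary date in SAP 9.3, transition-onset AEs have no clear by-phase home. The population concerned is about 160 Cohort 2 placebo completers, or about 180 with Cohort 1 if 10% dropout is assumed there. These are all the former placebo subjects expected to enter the switch, not a count of misclassified subjects or events.

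Two narrower errors follow from rules as written. An unscheduled laboratory value from about days 99–105 can displace a placebo subject's last DB value. Placebo subjects with altered titration would have wrong transition doses in the dose-based outputs if the nominal schedule is applied. The documents do not allow either group to be counted.

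Efficacy is unaffected. The rules should be settled before the database lock for the DB phase.

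**What to change.** 1. **Phase rule.** In SAP 3.3, 6.4, 9.3 and 9.4–9.6, assign AEs, laboratory values, vital signs and ECGs to OL on ganaxolone from each subject's first transition dose date (nominally day 64 in Cohort 1, day 99 in Cohort 2). This matches Protocol 9.5.3. End the Visit 5 window before that dose.
2. **Dose rule.** In SAP 3.3 and 9.1, use the dose recorded on the eCRF or study drug log for former placebo subjects, with the nominal schedule only where no record exists. Recode former ganaxolone subjects to 1800 mg/day unless the record shows reduced or missed dosing. The placebo-style titration that sites enter by instruction is not in itself such a record. Do not build the rule on capsule counts: SAP 9.1 says capsule-level accountability is not collected.
3. **Starting dose.** Reconcile SAP 3.3 and Protocol 9.1 (900 mg/day) with Protocol 9.4.5, Protocol Table 2 and the SAP 9.1 table (450 mg/day).

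A table of transition-onset AEs by prior arm would be useful but is optional. It should be labelled descriptive: only DB completers enter, so the groups are selected after randomisation and differ in prior exposure.

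The cost is SAP wording and minor programming, with no new data collection.
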